4 STUDY PROCEDURES

4.1 Screening and Randomization: Visit 0 (study day 0)

- Review of medical record
- Verbal informed consent (by phone)
- o Review of inclusion/exclusion criteria
- o For eligible participants:
- o Randomization to study condition: intervention or waitlist
- o Scheduling of baseline visit (Visit 1)

4.2 Study Baseline and Treatment Phase: Visits 1 through 14

All participating caregivers will complete study baseline measures in person on Visit 1/study day 1. Families will be asked to complete daily measures and have their child wear an actigraph to objectively measure sleep for a 14-day period. If families do not complete a diary on the appropriate day, they will be given the opportunity to complete the diary on another day during the 14-day period. For the intervention group, the Beds for Kids program bed delivery will occur 7 days after initiating the acitgraph. For the waitlist control group, the bed delivery will occur 14 days after initiating the actigraph. The daily visits (by phone) reflect the same procedures for each visit day, with the exception of bed delivery.

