3 INVESTIGATIONAL PLAN

3.1 General Schema of Study Design

3.1.1 Screening and Randomization Phase

Clinicians at the Chestnut Hill, South Philadelphia, Karabots, and Cobbs Creek locations who are already referring families directly to the Beds for Kids program will identify potentially eligible families for this study. Families who are eligible for Beds for Kids will then be asked whether they would be interested in participating in a research study related to the program. The clinician will provide the name, MRN, and contact information of interested families to the study team. The study team will then conduct an initial medical record review to identify whether the referred family is potentially eligible. The study team will then contact the potentially family to initiate informed consent and eligibility screening procedures. Alternatively, families receiving care at any of the CHOP primary care recruitment sites (Chestnut Hill, South Philadelphia, Karabots, or Cobbs Creek) may self-refer to the study if they hear of the Beds for Kids program through word-of-mouth or social

media (e.g., Facebook). However, we will not advertise the study on social media of any kind for recruitment purposes.

The informed consent process will take place by phone, with a member of the study team obtaining verbal consent from the legal guardian for study participation. Child assent will not be obtained as all participating children are under age 5 years. Families will be informed that they are free to decline to participate or to withdraw from the study, and that this will not impact their participation in the Beds for Kids program or any future medical care. After obtaining verbal informed consent, families will be screened for study inclusion and exclusion criteria.

Eligible families will be randomly assigned to receive a bed from Beds for Kids 7 days after initiating the actigraph/daily diary study procedures (intervention condition), or to receive a bed 14 days after initiating these procedures (waitlist control condition). Thus, this is a mixed between (bed vs waitlist) and within (days 0-7 vs days 8-14) group design.

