As bed delivery from the Beds for Kids program usually takes 1-2 weeks, this design does not interfere with the typical program practices and will not result in a bed delivery delay for participants in either condition. A member of the study team will call to schedule the family for their bed delivery, and to schedule a time to complete baseline measures.

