4.2.1 Visits 1 through 14 (study days 1 through 15 +1-7 days)

Visit 1 (in person):

- Completion of electronic caregiver-reported demographic information
- Completion of electronic caregiver-reported child sleep, child behavior, caregiver resilience, caregiver mood, and family chaos questionnaires
- Provision of incentive for baseline measure completion
- EMR review and data abstraction of child demographic information by a member of the study team.

Visits 2 through 15 (by phone): Visit 2 will occur within 7 days of Visit 1.

- Actigraphy (objective measurement of child sleep)
- Completion of caregiver daily mood and sleep questionnaires by phone

- Completion of caregiver-reported child behavior and sleep questionnaires by phone
- Bed delivery (day 7 after actigraph initiation for intervention condition; day 14 after actigraph initiation for waitlist control condition)
- Provision of incentives for daily measure and actigraph completion
- Scheduling of return of actigraph to study team (during the week following Visit 15)

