6.3.2 Efficacy Analysis

The primary analysis will be based on an intention to treat approach and will include all randomized subjects. To evaluate the impact of provision of a child bed through the Beds for Kids program on child sleep (Hypothesis 1a), we will compare children in the study condition who received a bed at day 7 to those in the waitlist control condition (bed at day 14) on objectively and subjectively measured sleep variables using two-level multilevel mixed models. Multilevel models allow for an examination of both within-child (daily assessments, level 1) and between-child (level 2) associations between sleep and daily child and/or caregiver functioning.²⁰ Child age, sex, baseline caregiver mood and resilience, and family chaos as level 2 covariates, given research showing that these variables impact child sleep. ^{7, 9, 12} To examine whether children who receive a bed at day 7 show improved behavior, increased caregiver mood, and better caregiver sleep relative to children in the waitlist condition (Hypothesis 1b), we will run three different multilevel mixed effect models, using child daily behavior, caregiver mood, and caregiver sleep scores as the outcomes, respectively. Analyses will include child sleep location, age, sex, baseline caregiver mood and resilience, baseline family chaos, and baseline child internalizing and externalizing behavior at model level 2 as covariates.

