9.1.2 Blinding

Families will not be blinded to condition assignment. The Lead Investigator [name], PI [name] and Study Coordinator [name] will not be blinded to condition assignment. However, all other members of the study team involved in data collection will be blinded to intervention group assignment. Blinding will be maintained by keeping a separate, password-protected list in REDCap that lists subject ID and group assignment. This database will be accessible only to the study statistician, PI ([name]), Lead Investigator ([name]), and Study Coordinator ([name]).

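### Caregiver-reported baseline covariates are collected after randomisation, probably with the arm known; the allocation should be held back until the Visit 1 questionnaires are in

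*Combined protocol and SAP*

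**What the plan says.** - **Order.** Section 4.1 lists "Randomization to study condition: intervention or waitlist" at Visit 0, followed by booking of the baseline visit. Table 1 also puts randomisation in the Visit 0 column. Section 4.2 then states: "All participating caregivers will complete study baseline measures in person on Visit 1/study day 1". Section 4.2.1 gives the content of that visit: "Completion of electronic caregiver-reported child sleep, child behavior, caregiver resilience, caregiver mood, and family chaos questionnaires".
- **Knowledge of the arm.** Section 9.1.2: "Families will not be blinded to condition assignment". Under section 3.1.1 the arms differ only in whether the bed comes 7 or 14 days after actigraph start, and a team member is to "call to schedule the family for their bed delivery, and to schedule a time to complete baseline measures".
- **Use of the ratings.** In section 6.3.2 the Hypothesis 1a models take "Child age, sex, baseline caregiver mood and resilience, and family chaos as level 2 covariates". The Hypothesis 1b models use these too and add, among others, baseline internalizing and externalizing behaviour.
- **Analysis set.** Section 6.3.2 takes an intention-to-treat approach covering everyone randomised. Section 3.3.2 ends recruitment once 50 dyads have completed follow-up.

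No section withholds the arm until the questionnaires are complete, and none plans an analysis without the caregiver-reported covariates.

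**The concern.** A covariate in a randomised comparison should be fixed before allocation, or at least be beyond its influence. Child age and sex come from the medical record and meet that test. Mood, resilience and chaos are caregiver self-reports, and child behaviour is a caregiver proxy report. All are collected after allocation. A caregiver expecting the bed in one week may answer differently from one expecting it in two. Adjustment would then carry that difference into the estimated treatment effect, and the trial's own data could not separate it from chance imbalance.

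The same ordering affects the analysis set. A family that drops out between Visit 0 and Visit 1 has been randomised but contributes nothing to the 14-day comparison.

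**Working it through.** **1. The plan's own figure.** Section 6.4 states 24 subjects for effect size 0.45, 14 measures, correlation 0.5, 80% power and p < .05. Reading 0.45 as Cohen's f for the between-group factor, lambda = N f² m / (1 + (m − 1) rho).
- N = 24: 24 × 0.2025 × 14 / 7.5 = 9.07 on 1 and 22 df; power 0.821.
- N = 22: 22 × 0.2025 × 14 / 7.5 = 8.32 on 1 and 20 df; power 0.783.

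The stated 24 is reproduced. It uses no covariates, so it does not depend on when the baseline is collected.

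**2. Sequence.** Randomisation (Visit 0) → call arranging delivery and baseline → questionnaires (Visit 1) → actigraph start, within 7 days of baseline (section 3.1.2) → bed at day 7 or day 14 from actigraph start. That the covariates follow randomisation is explicit. That the arm is known by then is inferred from the delivery call and the absence of family blinding.

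**3. Bias in a comparison of levels.** Let the outcome be Y = a + tau × arm + beta × X + error, with the reported covariate X* = X + delta × arm. Substituting X = X* − delta × arm, the coefficient on arm becomes tau − beta × delta, so the bias is −beta × delta. The documents give neither beta nor delta. The values below are assumptions, in SD units; the table shows the size of the bias.

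| slope beta | shift delta | bias (absolute) |
|---|---|---|
| 0.3 | 0 | 0 |
| 0.3 | 0.1 | 0.03 |
| 0.3 | 0.3 | 0.09 |

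A simulation of 4,000 trials per setting, with 25 per arm, one covariate, a person-level mean outcome and nominal 0.05, gave an adjusted type I error of 0.054 with slope 0.3 and no shift, and 0.065 with slope 0.3 and shift 0.3. At a steeper assumed slope of 0.5 and shift 0.3 it was 0.091. The unadjusted analysis stayed between 0.050 and 0.057 throughout.

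**4. Bias in a change contrast.** Take each child's week-2 mean minus week-1 mean. An additive covariate that is constant over days contributes beta × X* to both weeks and cancels. With balanced data the arm-by-week estimate is therefore the same with or without it, whatever delta is.

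**5. Early losses.** If a fraction p of dyads is lost between Visits 0 and 1 and there is no other loss, reaching 50 completers requires 50 / (1 − p) randomised. For assumed p:
- p = 0: 50 randomised, none lost.
- p = 5%: 50 / 0.95 = 52.6, so about 53, with 3 lost.
- p = 10%: 50 / 0.90 = 55.6, so about 56, with 6 lost.

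**6. Lead time if allocation waits for Visit 1.** Actigraphy starts 0 to 7 days after Visit 1, and the day-7 arm's bed comes 7 days after that: 0 + 7 = 7 to 7 + 7 = 14 days. Section 3.1.1 gives usual delivery as 1 to 2 weeks.

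**The case against.** The strongest reply is that the bias may never reach the primary result. Section 6.1 defines the endpoint as change and the abstract describes a mixed between and within design, so step 4 may be the relevant case. This stands as a condition. Section 6.3.2 does not specify an arm-by-week term, and the abstract also names a between-arm comparison over the second week, to which step 3 applies.

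The shift could also be near zero. At Visit 1 no child has the study bed, every family will receive one, and the arms differ by seven days of waiting. This stands too, so the range must include zero.

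Four stronger readings are tempting, and the documents do not support them:
- **That families are known to learn their arm before Visit 1.** The moment of disclosure is not stated.
- **That every baseline rating contaminates the primary sleep models.** Behaviour enters Hypothesis 1b but not 1a. Questionnaire child sleep is a covariate in neither. Aim 3 is an association pooled across conditions, not a randomised contrast.
- **That the per-covariate figure can be multiplied by five for Hypothesis 1b.** The slopes would be partial slopes of related measures, and the shifts could offset one another.
- **That early losses leave no data at all among 50 randomised.** The 50 are completers. Age and sex are in the medical record, and section 4.5.1 plans the Visit 16 procedures for withdrawals. What cannot be recovered is the 14-day outcome and the Visit 1 questionnaires.

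**Conclusion.** The point holds as a design weakness that is cheap to prevent. The caregiver-reported covariates are post-randomisation as a matter of record, and they are probably given with the arm known.

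The size of any bias is unknown. The 0 to 0.09 SD per covariate rests wholly on the assumed shift and slope, and it applies only if the analysis compares levels between arms. It is nil for an arm-by-week contrast with balanced data and additive, time-constant covariates.

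The early-loss point needs no assumption about reporting. Any dyad lost between Visits 0 and 1 belongs to the stated intention-to-treat set but cannot contribute to the 14-day comparison. How many there would be is an assumption. The planned sample size is unaffected.

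**What to change.** Amend sections 4.1 and 3.1.1 and the randomisation row of Table 1. Consent and eligibility stay at Visit 0, and the allocation is generated only after the Visit 1 questionnaires have been submitted. This also takes Visit 0 to 1 losses out of the randomised set. Assignment is 1:1, unblocked and unstratified, so the algorithm does not change.

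The cost is a short amendment and less lead time for arranging delivery in the day-7 arm (step 6). If that is too tight, the minimum is to keep generation at Visit 0 and withhold the arm from the family until the questionnaires are in, with the unblinded team members arranging delivery internally meanwhile. Losses before Visit 1 then remain in the randomised set and should be reported by arm. Under either option an unblinded team member should tell the family, so that the data collectors stay blinded as section 9.1.2 intends.

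If enrolment has progressed, prespecify a sensitivity analysis of the Aim 1 models adjusted only for child age and sex, and report losses between Visits 0 and 1 by arm. The week-1 value of a caregiver-reported outcome should not replace the dropped covariates, because it too is collected after randomisation and without blinding.

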4.2.1 Visits 1 through 14 (study days 1 through 15 +1-7 days)

Visit 1 (in person):

- Completion of electronic caregiver-reported demographic information
- Completion of electronic caregiver-reported child sleep, child behavior, caregiver resilience, caregiver mood, and family chaos questionnaires
- Provision of incentive for baseline measure completion
- EMR review and data abstraction of child demographic information by a member of the study team.

Visits 2 through 15 (by phone): Visit 2 will occur within 7 days of Visit 1.

- Actigraphy (objective measurement of child sleep)
- Completion of caregiver daily mood and sleep questionnaires by phone

- Completion of caregiver-reported child behavior and sleep questionnaires by phone
- Bed delivery (day 7 after actigraph initiation for intervention condition; day 14 after actigraph initiation for waitlist control condition)
- Provision of incentives for daily measure and actigraph completion
- Scheduling of return of actigraph to study team (during the week following Visit 15)

4.3 Follow-up Phase (only if applicable)

Caregivers will be contacted at one-month follow-up post-bed delivery (study day 36 [+1-7 days] for the intervention condition; day 43 [+1-7 days] for the waitlist control condition) to complete follow-up measures and a brief, semi-structured qualitative interview. The study will then end.

4.3.1 Visit 16: One month follow-up

- Completion of caregiver-reported child sleep and behavior follow-up questionnaires by phone or in-person.
- Option to consent for and complete in-person 30-minute semi-structured qualitative interview on sleep health and behavioral sleep treatments.

4.4 Unscheduled Visits

We do not anticipate any unscheduled visits as part of this study, although unscheduled phone contact may occur with some participants (e.g., clinically significant behavior/mood concern, issue with actigraph).

Clinically significant behavior/mood concern. Lead Investigator [name] will contact the family within 3 business days of the study visit if the family reported clinically significant child behavior or caregiver mood concerns on validated questionnaires. Similarly, if a caregiver spontaneously reports concerns related to caregiver or child behavior or mood by phone with a member of the study team, that team member will notify [name], who will then contact the family within 3 business days. During an unscheduled phone call, [name] will provide the family with appropriate community referrals for mental health services, as well as the information of the CHOP social workers employed at each of the primary care sites from which families were referred. In the case of clinically significant caregiver report of depressed mood, [name] will also conduct a risk assessment over the phone. This risk assessment will contain questions about caregiver homicidal and suicidal ideation, and the presence of any homicide/suicide plan or intent, consistent with CHOP behavioral health risk assessment practices. Should there be an imminent safety risk, [name] will contact emergency services (911 or Pennsylvania mobile crisis services) for further suicide/homicide/risk assessment. All information obtained during the risk assessment will be used only for the purposes of determining appropriate follow-up care. Information about child safety concern or mandated reporting will be documented in the child's medical record, and will not be stored with study data, or used for any study-related data analysis. It will not be stated in the medical record documentation that the child or caregiver are participating in a research study. For caregiver risk assessment procedures, risk assessment will be documented in a

Note to File coded by the participant ID and will be stored separately from the consent form and in a separate REDCap database used for tracking purposes only.

Actigraph issue. If there are any issues with the actigraph device, families will be encouraged to contact a member of the study team by phone. Any issues will be handled primarily via phone, although an in-person visit may occur if the family must be provided with a replacement actigraph.

Beds for Kids issue. If families encounter any difficulty with materials provided to them through Beds for Kids (e.g., mattress, bedframe), the family will be asked to contact Beds for Kids directly. We will inform families that in order to maintain their confidentiality and privacy in the study, we are unable to contact Beds for Kids on their behalf.

Other follow-up issue. If caregiver-child dyads that participated in the study contact the [name] (PI) or [name] (investigator) by phone to request follow-up, any issues will be handled via phone, without an in-person visit.

4.5 Subject Completion/Withdrawal

Subjects may withdraw from the study at any time without prejudice to their care. They may also be discontinued from the study at the discretion of the Investigator for lack of adherence to study treatment or visit schedules, or AEs. The Investigator may also withdraw subjects who violate the study plan, or to protect the subject for reasons of safety or for administrative reasons. It will be documented whether or not each subject completes the clinical study. If the Investigator becomes aware of any serious, related adverse events after the subject completes or withdraws from the study, they will be recorded in the source documents and on the CRF.

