This is a randomized controlled trial (RCT). Caregiver-child dyads will be assigned to the intervention group, in which they receive a bed through the Beds for Kids program after a 7-day period, or to the waitlist control group, in which they receive a bed after a 14-day period.

Setting/Participants:

This is a single site study to be performed at CHOP. A total of 50 caregiver-child dyads (child age 2 to 5 years) will be recruited from clinicians at CHOP primary care sites. Families must be eligible for the Beds for Kids program: (a) child is living without his/her own bed and (b) family is at or below 100 percent of the Federal Poverty Guideline.

Study Interventions and Measures:

Caregivers in the intervention and waitlist control conditions will complete measures of child sleep and behavior, as well as caregiver functioning (mood; resilience; sleep) and family functioning (i.e., chaos). Over a 14-day period, children in both study conditions will wear actigraphs to objectively measure sleep, and caregivers will complete daily ratings of child behavior, caregiver mood, and caregiver sleep. At one-month after bed delivery, caregivers will complete measures of child sleep and behavior. At one-month follow-up,

[figure not shown]
caregivers will also be given the option to participate in a brief, semi-structured qualitative interview related to barriers to and facilitators of sleep health and behavioral sleep treatment.

The primary study outcome is the difference between study conditions in actigraph-derived and caregiver-reported child sleep (bedtime, bedtime variability, sleep quality, night wakings, total sleep duration) for days 7 to 14 (bed vs control), as well as compared to baseline. Thus, this is a mixed between (bed vs waitlist) and within (days 1-7 vs days 8-14) group design.

TABLE 1: SCHEDULE OF STUDY PROCEDURES

Study Phase	Screening															One month Follow-up	
Visit Number	0	1	2	3	4	5	6	7	8	9	10	11	12	13	14	15	16
Approximate Study Days (May vary by 7 days)	0	1	2	3	4	5	6	7	8	9	10	11	12	13	14	15	36-43 (dependent on bed delivery date)
Chart review	X																
Verbal Informed Consent	X																
Review Inclusion/Exclusion Criteria	X																
Randomization	X																
Caregiver-reported caregiver and family demographic information		X															
Caregiver-reported child sleep and behavioral measures, caregiver resilience, mood, and family chaos measures		X															X

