3.3.2 Total Number of Study Sites/Total Number of Subjects Projected

This study will be conducted only at the Chestnut Hill, South Philadelphia, Cobbs Creek and Karabots, all of which are CHOP-affiliated primary care sites in Philadelphia, PA.

Recruitment will stop when 50 caregiver-child dyads (100 subjects total) have completed the full study procedures, through the follow-up period.

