4.5.1 Early Termination Study Visit

Subjects who withdraw from the study will have all procedures enumerated for Visit 16 at the early termination visit.

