7.1.2 Treatment Compliance and Adherence

Treatment compliance and adherence will be monitored by Lead Investigator [name] through contact with the Beds for Kids program. However, no members of the Beds for Kids program will have access to any study data from participants. [name] will monitor bed delivery scheduling and physical bed delivery in her capacity as Board Member of this organization.

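### Section 4.5 lets unblinded investigators discontinue families for poor adherence, and the nightly outcomes that the intention-to-treat analysis needs then stop being collected

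*Combined protocol and SAP*

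**What the plan says.** Section 4.5 (Subject Completion/Withdrawal) permits discontinuation from the study, not only from the intervention, "at the discretion of the Investigator for lack of adherence to study treatment or visit schedules". It adds: "The Investigator may also withdraw subjects who violate the study plan". Neither sentence gives a threshold or says which investigator decides. Sections 3.2 and 9.1.2 leave the PI, Lead Investigator and Study Coordinator unblinded, and section 7.1.2 says: "Treatment compliance and adherence will be monitored by Lead Investigator".

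Section 4.5.1 sets what is collected afterwards: "Subjects who withdraw from the study will have all procedures enumerated for Visit 16 at the early termination visit". Section 4.3.1 lists those procedures as caregiver questionnaires on child sleep and behavior plus an optional interview. Actigraphy and the daily diary are not among them.

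Section 6.3.2 states: "The primary analysis will be based on an intention to treat approach and will include all randomized subjects". The abstract defines the primary outcome as actigraph-derived and caregiver-reported sleep in the second week, compared between arms and with baseline.

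On numbers, section 3.3.2 says: "Recruitment will stop when 50 caregiver-child dyads (100 subjects total) have completed the full study procedures". The abstract (Setting/Participants) says: "A total of 50 caregiver-child dyads (child age 2 to 5 years) will be recruited".

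**The concern.** An intention-to-treat label protects the comparison only if outcomes are sought from everyone randomized, whatever their adherence. Here a stated rule lets someone who knows the arm end outcome collection because of behavior after randomization. A dyad removed early in the second week stays in the analysis set by name but adds little or nothing to the contrast between arms in change from week 1 to week 2. The mixed model uses the nights it has and treats the absent ones as ignorable given the recorded data. That can fail when the reason for removal is linked to whether the bed helped. The plan gives no missing-data method for such dyads and no sensitivity analysis, so a reader of the results could not tell whether it had failed.

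**Working it through.** **The plan's own figure.** Section 6.4 gives 24 subjects for an effect size of .45, 14 measures, correlation 0.5, 80% power and p<.05. For the between-groups test in repeated-measures ANOVA, λ = N·f²·m/(1+(m−1)ρ) = 24 × 0.2025 × 14 / 7.5 = 9.07 on 1 and 22 degrees of freedom. Power is 0.821, and N = 22 gives 0.783, so 24 reproduces. At N = 50, λ = 18.9 and power is 0.989. If f is diluted by 10% or 20%, power at 50 is 0.97 or 0.93. On the plan's own inputs, keeping non-adherent families in follow-up does not threaten power.

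**What the mixed model does when week 2 is lost.** A large simulation (6,000 dyads, weekly means, random intercept) set the benefit at 0.45 SD in adherers and zero in non-adherers, with 20% withdrawn before any week 2 data. These are all assumptions, and the 0.45 is a mean difference, not the f of section 6.4. The true intention-to-treat effect was 0.36. The model on all randomized dyads returned 0.45, as did completers alone. With withdrawn dyads followed, it returned 0.36. When withdrawal depended only on recorded week 1 sleep and the bed effect was uniform, there was no systematic bias (0.44 to 0.47 against 0.45 at 10 to 30% withdrawal).

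**How much depends on post-bed nights already recorded.** Non-use cannot be seen before the bed arrives, so some post-bed nights will usually exist.

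- Assumed: a fraction p of intervention children do not use the bed, gain nothing and are all withdrawn after k post-bed nights. All children have seven pre-bed nights, and the control arm is complete.
- From section 6.4: ρ = 0.5. With total variance 1, the between-child and nightly variances are both 0.5.
- Given seven pre-bed nights, the remaining variance of a child's own level is 0.5 × 0.5/(0.5 + 7 × 0.5) = 1/16. A mean of k post-bed nights adds 0.5/k. The total is (k+8)/(16k), so the child's weight is proportional to w(k) = k/(k+8), and w(7) = 7/15 = 0.4667.
- With d the benefit in bed users, the model estimates d·(1−p)·w(7)/[(1−p)·w(7) + p·w(k)]. The true effect is d·(1−p). The ratio is R = w(7)/[(1−p)·w(7) + p·w(k)].

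| k | w(k) | R, p = 10% | R, p = 20% |
|---|---|---|---|
| 0 | 0 | 1/0.9 = 1.11 | 1/0.8 = 1.25 |
| 2 | 2/10 = 0.200 | 0.4667/(0.4200+0.0200) = 1.06 | 0.4667/(0.3733+0.0400) = 1.13 |
| 4 | 4/12 = 0.333 | 0.4667/(0.4200+0.0333) = 1.03 | 0.4667/(0.3733+0.0667) = 1.06 |
| 7 | 0.4667 | 1.00 | 1.00 |

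**Number randomized.** Fifty completers need 50/0.90 = 55.6, so 56 randomized, at 10% attrition, and 50/0.80 = 62.5, so 63, at 20% (assumed rates). The abstract's 50 recruited agrees with section 3.3.2 only at zero attrition.

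**The case against.** The strongest reply is that the documents do not show removal falling on one arm. A reader might infer that non-adherence means not using the bed, that only intervention families can be non-adherent in the second week, and that removal must therefore inflate the effect. No section defines it so. Section 7.1.2 describes monitoring the scheduling and physical delivery of beds, which concerns both arms, and missed visits can occur in either arm. The diary records where the child sleeps (section 5.1.2), and section 6.3.2 uses sleep location as a covariate for Hypothesis 1b, which suggests that variation in bed use is expected within the analysis. This objection stands against any claim of a fixed direction.

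A reader might also infer that recruiting to 50 completers replaces non-adherers with adherers and so turns the result into a completers' result. Section 3.3.2 removes nobody from the analysis, and further families are randomized 1:1. The stopping rule does not itself bias the comparison, although it can make attrition less visible.

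There are safeguards: completion status is documented (section 4.5), missed diaries can be made up (section 4.2), families are paid daily and for complete data (section 9.7.3), and the withdrawal clause is permissive. These should reduce missing data. None of them limits a discretionary removal or restores nightly data after it.

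**Conclusion.** The point holds as a conflict between sections. Section 4.5 allows discretionary, unblinded discontinuation from the study for poor adherence, and sections 4.3.1 and 4.5.1 then collect no nightly data. Section 6.3.2 nonetheless relies on nightly data from all randomized dyads.

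The size and direction of any bias cannot be determined, because no withdrawal or non-use rate is given. Under the assumptions in the working, the overstatement is 3 to 6% with four post-bed nights recorded and 6 to 13% with two. The 11 to 25% figure is a ceiling that requires no post-bed nights at all, and should not be read as an estimate. If withdrawal depends only on recorded data in the model and the bed effect is uniform, there is no bias. If the families removed were those who benefited more than average, the effect would be understated.

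The mismatch between 50 recruited and 50 completed is a separate matter of consistency.

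**What to change.** In section 4.5, state that non-adherence to the bed or to visits is recorded but does not end actigraphy or diary collection unless the family withdraws consent. Leave the safety wording unchanged. Add that withdrawals initiated by an investigator will be reported by arm with reasons.

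Separately, state the number to be randomized and bring the abstract, section 3.3.2 and section 6.4 into line with it.

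The cost is protocol wording. The small downside is that some families with sparse data stay in follow-up.
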